## 6.3 Procedure Assessments

Immediately prior to introducing a guide catheter, the physician will perform an angiogram of the affected intracranial artery. The angiogram will be done using standard techniques (subtracted complete runs from arterial to venous phase initially and at end of procedure). The purpose of the pre-procedure angiogram is to confirm:

- the location of the occlusion;
- that the subject remains suitable for treatment with mechanical thrombectomy;
- that the subject remains a candidate for the study per the eligibility criteria.

In the event that the subject is excluded as a result of the angiogram, the subject will be considered a screen-failure and will not require any study follow-up.

Subjects will have challenging occlusions, with mTICI  $\leq$  2a post one, or two passes, of another Mechanical Thrombectomy device. Any commercially available Mechanical thrombectomy device (i.e. either aspiration or Stent-retriever other than NIMBUS) may be used during the first and up to two vessel clearance attempts. The physician may use his own discretion on whether to introduce the NIMBUS after one failed vessel clearance attempt, or after two. The NIMBUS must be used no later than the overall third procedural pass for the patient to be eligible. Up to 50 subjects will be treated with the NIMBUS.

Once the decision has been made to use NIMBUS, it is used for up to three passes. After the third pass with the NIMBUS, if the physician would like to utilize another device/technique for treatment, they may. Angiographic imaging will be collected per every pass for subsequent review by an independent Imaging Core Lab. Clot will also be collected per every pass for analysis in an independent Central Lab.

Endovascular treatment with NIMBUS, and the other stent-retrievers, is performed per hospital standard technique and in accordance with the applicable devices' IFU.

The following data will be captured during the procedure, and recorded on the eCRF:

- Name of the treating physician.
- Type of sedation used.
- Vessel location of the occlusion being treated per pass.
- mTICI scores per pass (Pre-device deployment and post-device retrieval).
- Names and sizes of stent-retrievers used per pass.
- Lot number of NIMBUS used, as applicable.
- Ancillary devices used (e.g., balloon guides, microcatheters) per pass.
- Details of the technique used per pass.
- Relevant time points during the procedure (e.g. arterial puncture time).

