#### 7.5.1 Primary Endpoint Analysis

- **Successful Revascularization (mTICI  $\geq 2b$ ) with NIMBUS as determined by an Independent Core Lab.**

The primary endpoint is successful revascularization after the final pass of NIMBUS, where the successful revascularization is defined as an mTICI score of 2b or greater.

The number and percentage of subjects with a procedural mTICI score  $\geq 2b$  following the final pass of NIMBUS will be summarized, excluding mTICI scores from other devices applied after the final pass with NIMBUS.

Subjects with a missing mTICI score (from the imaging core lab) for the final pass using Nimbus, will be imputed with the final (end of procedure) mTICI score from the imaging core lab if the final pass using Nimbus is the last procedural pass, there were no post mechanical thrombectomy interventions and no intra-arterial thrombolytic agent performed after the final Nimbus pass.

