#### 7.5.2 Secondary Endpoint Analyses

##### 1. **Successful Procedural Revascularization (final mTICI $\geq 2b$ )**

The number and percentage of subjects with a final (end of procedure) mTICI score  $\geq 2b$  will be summarized.

Subjects with a missing mTICI score (from the imaging core lab) at the end of procedure will be imputed with the non-missing mTICI score from the last procedural pass (e.g., pass 1 to 10) from the imaging core lab if there were no post mechanical thrombectomy interventions and no intra-arterial thrombolytic agent performed after the final procedural pass.

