### 7.9 Subgroup Analysis

The primary endpoint will be analyzed by subgroups with clinically meaningful risk factors using the mITT analysis set. Additional subgroup analyses may be performed as applicable. Descriptive statistics (continuous summary measure for the mTICI score) for each subgroup will be presented when there is a minimum of 10 subjects in all subgroup levels, CIs will not be provided due to limited sample size.

- Clot composition: Tough clot vs. Other clot
- Nimbus first use: Procedural Pass 2 vs. Procedural Pass 3
- Vascular location:
- Balloon guide catheter (BGC) usage: BGC used vs. BGC not used

Subjects who used BGC are defined as those who used BGC at least once during procedure; otherwise subjects will be classified as no use of BGC throughout the procedure.

- Use of BGC and/or IC: BGC with IC, BGC without IC vs. no BGC
  - BGC with IC – subjects who used BGC and IC at least once during procedure;
  - BGC without IC – subjects who used BGC at least once, but none with IC during procedure;
  - No BGC – subjects who didn't use of BGC throughout the procedure.

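### SAP 7.9 labels the balloon-guide and intermediate-catheter subgroups by use at any time in the procedure, so exposure can be assigned after the primary endpoint is fixed and can create a false association

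*SAP*

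**What the plan says.** **Outcome.** SAP 7.9 states: "The primary endpoint will be analyzed by subgroups with clinically meaningful risk factors using the mITT analysis set". SAP 7.5.1 fixes that endpoint after the last NIMBUS pass, "excluding mTICI scores from other devices applied after the final pass with NIMBUS".

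**Exposure.** SAP 7.9 counts BGC use anywhere in the procedure: "Subjects who used BGC are defined as those who used BGC at least once during procedure". The three-level split works the same way. BGC with IC means "subjects who used BGC and IC at least once during procedure", and the two catheters need not be used on the same pass. I read IC as intermediate catheter, following the list in SAP 7.4.

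**Later passes.** Protocol 6.3 says: "Once the decision has been made to use NIMBUS, it is used for up to three passes". It then says: "After the third pass with the NIMBUS, if the physician would like to utilize another device/technique for treatment, they may". At most two passes precede NIMBUS, so with consecutive use NIMBUS ends by overall pass 5 (2 + 3). SAP 7.5.2 gives passes 1 to 10 as its example range.

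**Data.** Protocol 6.3 has the eCRF record "Ancillary devices used (e.g., balloon guides, microcatheters) per pass". SAP 7.4 already plans catheter summaries per pass, with NIMBUS passes shown separately.

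**Display.** SAP 7.9 gives descriptive statistics only, without confidence intervals, and only if every subgroup level holds at least 10 subjects. SAP 4 plans no hypothesis tests.

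**The concern.** A subgroup variable should be settled before the outcome it is set against. Here the outcome stops at the final NIMBUS pass, but the label stays open until the procedure ends. Passes after NIMBUS should occur mainly when NIMBUS did not succeed; that is an inference, but a natural one. Take a BGC case in which NIMBUS fails and an IC is first used on a later pass. It moves from BGC without IC to BGC with IC and takes its failure along. A success that ends at the final NIMBUS pass cannot move.

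The SAP guards against this on the outcome side: it drops later-device scores, and it bars imputation of the NIMBUS score when other treatment followed. The exposure side has no matching rule.

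At stake is a contrast in technique that comes partly from the classification. SAP 7.9 presents these factors as clinically meaningful, and Protocol 2 says the effectiveness rate will be considered in designing further studies.

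**Working it through.** **The plan's own figure.** Protocol 9.6 and SAP 6: 1.96 × √(0.86 × 0.14 / 45) = 10.14%, so the stated 10.1% reproduces. SAP 7.9 gives no figure for the subgroups.

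**Inputs**
- s, success after the final NIMBUS pass: 0.86 (SAP 6).
- a, share using an IC by the final NIMBUS pass, independent of outcome: 0.50 (assumption).
- q, share of unexposed failures who first receive an IC later: 0 to 0.50 (assumption).
- c, share of unexposed successes who first receive an IC later: 0 at first (assumption).
- No true effect of IC.

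**Formulas**, applied among BGC users:
- Success with IC = s[a + (1−a)c] / {s[a + (1−a)c] + (1−s)[a + (1−a)q]}
- Success without IC = s(1−c) / [s(1−c) + (1−s)(1−q)]

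**Results with c = 0**

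| q | With IC | Without IC | False gap (points) |
|---|---|---|---|
| 0 | 86.0% | 86.0% | 0 |
| 0.10 | 0.43/0.507 = 84.8% | 0.86/0.986 = 87.2% | 2.4 |
| 0.25 | 0.43/0.5175 = 83.1% | 0.86/0.965 = 89.1% | 6.0 |
| 0.50 | 0.43/0.535 = 80.4% | 0.86/0.930 = 92.5% | 12.1 |

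The group without BGC stays at 86.0% if BGC use does not change during the procedure.

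**Other values**
- With a from 0.70 down to 0.30, the gap is 4.4 to 9.6 points at q = 0.25 and 9.0 to 18.5 at q = 0.50.
- At s = 0.63 (the low end after a set number of passes in Protocol 1.2.1) and a = 0.50, it is 11.8 points at q = 0.25 and 24.1 at q = 0.50.
- If successes can also drift, at s = 0.86, a = 0.50 and q = 0.50:
  - c = 0.10: 0.473/0.578 = 81.8% against 0.774/0.844 = 91.7%, a gap of 9.9 points.
  - c = 0.25: 0.5375/0.6425 = 83.7% against 0.645/0.715 = 90.2%, a gap of 6.6 points.

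**How few subjects this takes.** In 45 subjects, 45 × 0.14 = 6.3 failures are expected. If 66% use a BGC (assumption), 45 × 0.66 = 29.7 are BGC users, and 29.7 × 0.5 × 0.14 × 0.5 = 1.04 subjects move. So about one reclassified failure produces the 12.1 points. The chance standard error of a gap between two groups of 14.85 is √(0.1204 × 2/14.85) = 12.7 points.

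**Would counting all NIMBUS passes be enough?** Not fully, because failures tend to have more NIMBUS passes. As an illustration, suppose successes stop after one NIMBUS pass, failures have three, and 25% of unexposed subjects switch to an IC on each extra pass. Then 1 − 0.75² = 43.75% of unexposed failures become exposed. The rates are 0.43/0.5306 = 81.0% and 0.86/0.9388 = 91.6%, a gap of 10.6 points. A label fixed at the first NIMBUS pass cannot be changed by its result.

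**The case against.** **The documents show that the bias is possible, not that it occurs.** No section says how often an IC or BGC is first used after the final NIMBUS pass, and if that never happens the gap is zero. A reader might infer that the rule does produce a false association of 12 points or more. The text does not support that, and the late-exposure shares above are assumptions.

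**BGC is the weaker case.** Protocol 1.3.6.1 advances the guide, sheath or balloon guide before NIMBUS, and 1.3.6.3 withdraws NIMBUS into the guide. First BGC use after NIMBUS would mean a late change of the access system. This stands; the concern rests mainly on IC.

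**Successes can drift too.** Protocol 6.3 attaches no mTICI condition to later devices, and a 2b result counts as success yet falls short of the 2c secondary endpoint. This stands and shrinks the gap, as shown. A reader might infer that only failures can be relabelled; the documents do not say so.

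**Use before NIMBUS.** Catheters used only in the one or two earlier passes also count. That blurs exposure, but it does not depend on the NIMBUS outcome and adds nothing to this bias.

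**Little hangs on the display.** There are no tests or intervals, a three-level split of about 45 to 50 subjects may miss the minimum of 10, and chance variation is already as large as the false gap. SAP 7.9 also describes a continuous summary of mTICI, so the percentage gap may not be the statistic shown. These points limit the harm but do not justify the label.

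**Rescue therapy.** Protocol 6.3.1 calls it not applicable. That does not close off later exposure, since Protocol 6.3 and SAP 7.5.1 both provide for other devices after NIMBUS.

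**Conclusion.** The concern holds as a flaw in definition. The rule in SAP 7.9 lets BGC and IC labels be set after the primary endpoint, and plausibly more often in failures. The likely direction, through IC, is to worsen BGC with IC and flatter BGC without IC.

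At the planned success rate the expected false gap runs from 0 to 12.1 points for late IC exposure in 0% to 50% of unexposed failures. This assumes 50% IC use by the final NIMBUS pass, no true effect and no late exposure in successes. It is a bias in an exploratory description. No error rate is affected, and the overall primary endpoint result is untouched. The change is worth making because nothing in the documents argues for the whole-procedure label and the correction is cheap.

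**What to change.** In SAP 7.9, define the BGC and BGC/IC subgroups by the equipment used on the first NIMBUS pass, taken from the per-pass eCRF fields. Optionally add classification over all NIMBUS passes as a sensitivity display, with a note that it keeps some bias because failures tend to have more NIMBUS passes.

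The cost is a sentence or two in the SAP and no new data. The small downside is that catheter changes on later NIMBUS passes are not reflected in the main label.

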### 7.10 Additional Analyses

Unless specified otherwise, the following events will be analyzed using the mITT Analysis Set.

- Device deficiency

Subjects with at least one device deficiency data from CRF will be listed.

- Protocol deviations

The number of deviations, the number and percentages of subjects with any protocol deviation will be summarized overall and by deviation category.

- NIH Stroke Scale (NIHSS) total score

The NIHSS total score and change from baseline will be summarized at the scheduled visits with observed data.

- mTICI scores

All mTICI scores will be summarized by pass and at the end of study procedure using the assessments from the core lab.

- First pass effect using NIMBUS

To investigate the first pass effect using NIMBUS, the number and percentage of subjects by mTICI score(including combinations of  $mTICI \geq 2b$ ,  $mTICI \geq 2c$ ) following the first pass of NIMBUS will be summarized using the assessments from the core lab.

A shift table of mTICI scores from pre-first NIMBUS pass to post-final NIMBUS pass will be summarized, excluding the end of procedure mTICI scores.

Similarly, a shift table of mTICI scores before and after the first NIMBUS pass will be summarized as well.

#### 7.11 Changes from the Planned Analyses

- Analysis window mRS  $\leq 2$  at 90-day

Due to the potential impact of Covid-19, it is expected that there may be more late 90-day mRS assessments compared to the SAP-defined 90-day window of  $\pm 14$  than anticipated. In order to minimize the impact of out of 90-day window assessments, analyses on mRS endpoint will include all available assessments on or after 76 days. Analyses using the 90-day window of  $\pm 14$  days will be considered part of the sensitivity analyses (section 7.8).

Other study endpoints at 90 days (e.g., all-cause mortality at 90 days) are not impacted by the 90-day window as other endpoints are not restricted by the compliance of the 90-day visit.

End of Document
